### 3.3 Dose Limiting Toxicity (DLT) Definition

A DLT will be defined as:

- Any death not clearly due to the underlying disease or extraneous causes
- Any grade 3 or higher non-hematologic toxicity
- Liver function abnormalities meeting Hy's law
- Neutropenic fever
- Grade 4 neutropenia or thrombocytopenia > 7 days
- Grade 3 or higher thrombocytopenia with bleeding

- Grade 3 or higher nausea/vomiting or diarrhea  $\geq$  72 hours with adequate antiemetic and other supportive care
- Grade 3 or higher fatigue  $\geq$  1 week
- Grade 3 or higher electrolyte abnormality that lasts  $>72$  hours, unless the patient has clinical symptoms, in which case all grade 3 or higher electrolyte abnormality regardless of duration should count as a DLT.

All AEs of the specified grades should count as DLTs except those that are clearly and incontrovertibly due to disease progression or extraneous causes.

The decision to open the Phase II window part of the trial will be made after RP2D has been established. All Safety Data will be reviewed by the Principal investigator and will be used to determine whether the study proceeds to the “window” Phase II trial in the neo-adjuvant setting.

### **3.4 Phase II Component (Window/Neo-adjuvant Cohorts)**

The “window” component of the trial evaluates the combination of pre-operative palbociclib plus letrozole followed by the addition of hydroxychloroquine (HCQ) for postmenopausal patients with Stage I-III estrogen receptor-positive and HER2-negative breast cancer (Figure 2).

Correlative studies using baseline and follow up breast biopsies and blood work are included in the overall research grant. The Phase II portion will assess the change in the percentage of all patients who achieve CCCA when adding HCQ to the palbociclib/letrozole combination.

### **3.5 Phase II Window/Neo-adjuvant Component – Dose Cohorts (Parts 1 and 2)**

To estimate the dose responsiveness of HCQ in the main outcome measures as stated on Section 2.2.3, two groups will be enrolled at the HCQ levels as shown below:

Dose Level Groups	Number of patients	Hydroxychloroquine dose	Letrozole dose	Palbociclib dose
Part 1	6	400 mg/d p.o.	2.5 mg/d p.o.	75 mg capsule p.o. daily continuously, 28-day cycle
Part 2	30	RP2D		

An initial group of 6 patients (part 1) will be enrolled at an HCQ dose of 400 mg daily sequentially, and then a second group of 30 patients (part 2) will be enrolled at the HCQ dose defined in the Phase I portion as RP2D. The main efficacy endpoint statistical plan is based on the 30 patients enrolled in part 2 as described in Section 8.0.

The dose of palbociclib for both parts 1 and 2 is fixed at a dose of 75 mg orally daily continuously without a break. Letrozole and palbociclib are given for the first 2 weeks, then after the second biopsy (T2), HCQ at the assigned dose will be added. After 4 weeks (2 weeks of HCQ) (T2), the primary endpoint will have been obtained with analysis of the surgical specimen (or research biopsy at that timepoint if additional neoadjuvant endocrine therapy or chemotherapy is indicated as standard of care. Details on dosing and dose adjustments are shown in Sections 6.1.4 and 6.2.3. Using the same population, treatment and biopsy schema, 30 patients will be enrolled for the phase II Stage 2 portion of the trial.

### **3.6 Phase II Patient Evaluability**

Patients who meet the eligibility criteria and complete a full 4 weeks of therapy (14 days of low-dose palbociclib plus letrozole and 14 days of dose palbociclib plus letrozole with HCQ) will be considered evaluable for Phase II. In addition, the completion of biopsies at T0, T1 and T2 with interpretability of Ki67 are required for evalutability. Baseline Ki67 >5% is required to enhance the interpretability of CCCA fraction change from T1 to T2.

### **3.7 Replacement of Patients**

Patients who are not evaluable for dose-limiting toxicity in the Phase I portion and those not evaluable for Ki67 at T0, T1 and T2 in the Phase II portion will be replaced.

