### 2.2.3 Phase II Part 2 Primary Objective and Endpoints

To determine whether hydroxychloroquine added to low dose palbociclib and letrozole can increase the proportion of patients whose tumors achieve complete cell cycle arrest (CCCA, defined as the Ki67  $\leq$  2.7%) comparing T2 to T1 as shown in Figure 2, see Section 5.3.4).

The primary endpoint is the increase in percentage of all patients who achieve CCCA with low dose palbociclib and letrozole (at week 2, time T1) compared to that of low dose palbociclib and letrozole with the addition of HCQ (at 5 weeks, day 29, time T2).

A previously conducted trial of neoadjuvant aromatase inhibitor (anastrozole) plus standard dose palbociclib estimated the CCCA probability to be 44% with aromatase inhibitor alone and powered their study to detect a 50% increase of 44% to 66%. A 26% CCCA probability was seen with anastrozole alone and 86% with the addition of standard dose palbociclib. We will aim for a CCCA reference probability of 50% with low-dose palbociclib + letrozole (T1) and a CCCA probability of 75% with the addition of HCQ (see Section 8 for statistical plan and samples size calculations for the Phase II portion).

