### Hydroxychloroquine Dose Escalation Scheme

Dose Level (DL)	Hydroxychloroquine	Letrozole	Palbociclib
0 (Starting Dose)	400 mg/d	2.5 mg daily	75 mg daily (continuous)
+1	600 mg/d		
+2	800 mg/d		

The dose escalation portion will use a 3+3 dose escalation design to evaluate escalating dose levels of HCQ in combination with palbociclib and letrozole (see dose level table above). Three patients will be enrolled at the first dose level (DL 0, 400 mg daily) of the triplet combination. At least 3 patients must complete a treatment cycle (28 days) with the triple combination and undergo toxicity assessment before any additional patients are enrolled into higher dosing cohorts. Intrapatient dose escalation or change of dosing schedule is not allowed. At least 6 evaluable patients are to be treated at a dose level for a RP2D to be declared.

- If 0 out of 3 patients in a dose level experience a DLT in the defined timeframe another 3 patients will be enrolled at the next higher dose level.
- If no more than 1 patient experienced a DLT at a dose level, then more patients will be added to that cohort to increase the cohort up to six patients at the same dose level
- If no more than one of the first 6 patients treated experiences a DLT, then 3 patients will be enrolled at the next higher dose level.
- If two or more of the first 6 patients treated within a cohort experience DLT, then this dose level will be considered not tolerated and the dose escalation will be halted. If two DLTs are seen in any cohort, no further patients will be enrolled at that level and next level lower will be declared the RP2D.

The RP2D is defined as the highest dose level at which 6 patients have been treated with at most 1 instance of DLT.

If two DLTs are seen at the starting dose of 400 mg (DL 0), then this treatment will be declared to not be feasible as doses of HCQ < 400 mg may be too low for the intended effects.

The Principal Investigator will monitor safety throughout the study, review patient data and make decisions prior to advancing to the next dose level, approve dose escalation, and will also declare the establishment for RP2D and declare when the Phase II part of the study can commence.

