#### **6.2.3 Dosing of hydroxychloroquine and dose adjustments for hydroxychloroquine**

HCQ will be given by mouth at the assigned dose for the Phase I dose escalation and Phase II fixed dose parts of the trial. The dose of 400 mg daily was chosen as the starting dose for the Phase I portion as this is the usual dose used clinically and has been combined with endocrine and other and cancer therapies at this dose in prior studies.P34-37P There will be no dose adjustments for HCQ, and any grade 3 toxicity that is attributed to HCQ will require discontinuation of drug and for the patient to come off study. Subsequent treatment will be as per standard of care. For patients on the Phase I portion, any Grade III toxicity attributed to HCQ will also be counted as a dose-limiting toxicity if occurring in the first 28 days.

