### **Phase II:**

The Phase II portion will be performed in a different population of patients (early stage) in the pre-operative setting. In order to obtain qualitative information about the dose responsiveness of HCQ when added to letrozole and palbociclib, Part 1 of the Phase II portion will enroll 6 patients at an HCQ dose of 400 mg (if in fact, the RP2D is 600 or 800 mg). Following this, Part 2 will be conducted at the RP2D for HCQ based on the primary endpoint of proportion of patients achieving tumoral CCCA, with the formal statistical plan using a 2-stage Simon optimal design and looking to increase the CCCA rate from 50% with low dose palbociclib + letrozole to 75% after the addition of HCQ. This design requires 11 patients in the first stage and 14 patients in the 2nd stage. It would stop after the 1st stage if no more than 6 patients show CCCA by tumor biopsy after HCQ treatment and declared the treatment as promising if at least 17 out of 25 total evaluable patients exhibit CCCA.

This design has alpha = 4%, 81% power, and a probability of 0.73 of terminating after the 1st stage if the true CCCA rate=50%. For the group of patients at the RP2D, we therefore plan a sample size of 30 patients over 12-15 months, accounting for patient dropout (including those with Ki67 >10% at T1). We have a large eligible patient population and have led national accruals in other multi-center neoadjuvant endocrine trials in post-menopausal women (e.g. ALTERNATE Trial). In addition, recent local experience of conducting window of opportunity trials in this setting have demonstrated the feasibility of accrual at a rate of ~2 patients per month. Thus, we expect to achieve accrual goals.

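### The 17-of-25 rule measures complete cell cycle arrest (CCCA) among Part 2 patients who completed HCQ, not among all patients, because those who start HCQ and leave for toxicity are replaced

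*Combined protocol and SAP*

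**What the plan says.** All references are to the combined protocol and SAP.

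- **Endpoint (Section 2.2.3).** "The primary endpoint is the increase in percentage of all patients who achieve CCCA", comparing T1, before HCQ, with T2, after it. Sections 3.1 and 3.4 also refer to all patients.
- **HCQ toxicity (Section 6.2.3).** "any grade 3 toxicity that is attributed to HCQ will require discontinuation of drug and for the patient to come off study".
- **Leaving early (Section 5.2.5 and Table 2).** The patient returns for the off-study assessments. The off-study column of Table 2 has no biopsy.
- **Evaluability (Section 3.6).** The patient must complete four weeks of therapy, 14 days of them with HCQ, and have an interpretable Ki67 at T0, T1 and T2.
- **Replacement (Section 3.7).** "those not evaluable for Ki67 at T0, T1 and T2 in the Phase II portion will be replaced". The reason for the missing value plays no part.
- **Decision (Section 8.0, Phase II).** The design "declared the treatment as promising if at least 17 out of 25 total evaluable patients exhibit CCCA".

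No section gives an analysis of all patients who started HCQ, and none says how a starter without T2 is to be counted. Section 3.5 ties the efficacy plan to the 30 enrolled patients but refers to Section 8.0, which decides on 25 evaluable ones.

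**The concern.** Two different kinds of missing T2 are treated alike. An inadequate or unreadable core is plausibly unrelated to whether HCQ works, and replacing that patient does little harm. A T2 that is missing because HCQ was not tolerated is a consequence of the drug under test. Replacing that patient removes an unfavourable outcome from the denominator. The trial has one arm and a fixed 50% reference, so no control group undergoes the same selection.

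At stake is what a positive result means. A reader of Section 2.2.3 would take 17 of 25 as the CCCA rate to expect when HCQ is added to low-dose palbociclib and letrozole. The rule supports that reading only for patients who got through the two weeks of HCQ.

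**Working it through.** **Inputs (Section 8.0, Phase II)**
- Rates: "looking to increase the CCCA rate from 50% with low dose palbociclib + letrozole to 75% after the addition of HCQ".
- Stages: "This design requires 11 patients in the first stage and 14 patients in the 2nd stage".
- Futility: "It would stop after the 1st stage if no more than 6 patients show CCCA by tumor biopsy after HCQ treatment".
- Success: at least 17 of 25 evaluable.
- Stated properties: alpha 4%, power 81%, probability 0.73 of stopping after stage 1 when the rate is 50%.

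**Step 1. Reproduce the design.** With X1 the stage 1 count and p the CCCA rate in the patients counted,

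P(success) = sum over x = 7 to 11 of P(X1 = x) × P(Bin(14, p) ≥ 17 − x), where X1 ~ Bin(11, p).

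- p = 0.50: P(X1 ≤ 6) = 0.726 and P(success) = 4.58%.
- p = 0.75: P(success) = 80.05%.

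The early stopping probability agrees with the plan, and power agrees to within a point. Alpha computes to 4.6% rather than 4%, which is a separate small correction.

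**Step 2. Count the replaced starters.** Let k be the number of HCQ starters lost to toxicity and replaced. The documents give no value for k, so k = 1 and k = 2 are assumptions. A just-positive trial has 17 CCCA among 25 evaluable patients, and among all starters the rate is 17/(25 + k).

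| k | CCCA / HCQ starters | Rate | Exact two-sided 95% CI |
|---|---|---|---|
| 0 | 17/25 | 68.0% | 46.5% to 85.1% |
| 1 | 17/26 | 65.4% | 44.3% to 82.8% |
| 2 | 17/27 | 63.0% | 42.4% to 80.6% |

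**Step 3. Chance of success if the all-starter rate is 50%.** If lost starters count as not CCCA and make up k of every 25 + k starters, the rate among evaluable patients is 0.50 × (25 + k)/25. Put this into the formula of Step 1.

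| k | Evaluable rate | P(success) |
|---|---|---|
| 0 | 0.50 | 4.6% |
| 1 | 0.52 | 6.8% |
| 2 | 0.54 | 9.8% |

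These probabilities concern a claim about all starters. If the rate among evaluable patients is itself 50%, the error is 4.6% whatever k is.

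**Step 4. Would a lower-bound condition on the starters' rate help?** The exact one-sided 95% lower bound for 17/25 is 49.6%. Requiring a bound above 50% would therefore fail a result that meets the plan's own rule with nobody lost. With no loss the requirement becomes 18 of 25 (lower bound 53.8%). Power at 75% then falls from 80.1% to 70.1%, and alpha to 2.0%.

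**The case against.** The best defence is that an evaluable set suits a short pharmacodynamic question and that Sections 3.6 and 8.0 state it openly. HCQ intolerance would not be hidden either: safety is a secondary objective in Section 2.2.4, and Section 8.1 requires toxicity and efficacy summaries every six patients. This stands as a reason to keep 17/25 as the decision rule. It does not reconcile that rule with the all-patients wording, and it supplies no CCCA rate for starters.

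A T2 value may exist after all, since Section 3.5 allows the surgical specimen to provide it. Such a patient would still be non-evaluable under Section 3.6 because she did not complete 14 days of HCQ. Whether Section 3.7 replaces her is unclear, because it speaks only of evaluability for Ki67. That is another reason to clarify the text.

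Three stronger readings are tempting and are not supported.

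- **The trial's type I error is inflated.** It is not, for the quantity that Section 8.0 tests. The 6.8% and 9.8% apply only when lost starters count as failures, and the plan does not say that its 50% reference was set on that footing.
- **Five of 30 patients could be lost to HCQ.** The five in Section 3.8 are dropouts from all causes. Section 8.0 includes among them patients with T1 Ki67 above 10%, who leave before HCQ under Section 5.2.3.2. Nor does the Phase I ceiling supply a rate. "The RP2D is defined as the highest dose level at which 6 patients have been treated with at most 1 instance of DLT" concerns metastatic patients over 28 days and counts toxicity not limited to HCQ, whereas Phase II gives HCQ for 14 days before T2.
- **Replacement favours the RP2D over 400 mg.** The same rule covers Part 1, which has six patients and a comparison that Section 8.0 describes as qualitative. The documents do not show a direction.

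**Conclusion.** The concern holds as a mismatch between the stated endpoint and the population the rule describes. Sections 3.6, 3.7 and 8.0 together make 17/25 a statement about patients who completed HCQ, and no analysis answers the all-patients question in Section 2.2.3.

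The effect is nil if no starter is lost. Under the assumed loss of one or two, the rate at a just-positive result is lower by 2.6 points (68.0 − 65.4) or 5.0 points (68.0 − 63.0), and the chance of success at a true all-starter rate of 50% is 6.8% or 9.8% instead of 4.6%. These figures rest on counting a starter without T2 as not CCCA, which is the natural reading of a percentage of all patients who achieve it. They are illustrations, not forecasts. The matter should be settled before results are known, but it does not invalidate the Simon design for evaluable patients.

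**What to change.** In Sections 3.7 and 8.0:

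1. Separate a technically inadequate or unreadable sample, where the patient may be replaced, from a T2 missing because of toxicity, progression or withdrawal after at least one HCQ dose.
2. Keep 17 of 25 evaluable patients as the Simon decision rule.
3. Add a named analysis of all Part 2 patients who started HCQ at the RP2D. Count a T2 missing for those treatment-related reasons as not CCCA, and report the rate with an exact confidence interval beside the 17/25 result.
4. State that the 17/25 conclusion applies to patients who completed HCQ, and align the wording of Section 2.2.3 with this.

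Do not make success depend on a lower bound above 50% for the starters' rate; Step 4 shows that 17/25 itself would fail.

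The cost is wording and one further analysis of data already held. The reported CCCA rate will be slightly less favourable if any starter is lost. If the sponsor prefers the HCQ-started set for the decision itself, the boundaries and power must be recomputed. With the present boundaries and 75% CCCA in completers, the starters' rate is 0.75 × 25/26 = 72.1% or 0.75 × 25/27 = 69.4% for one or two losses, and power falls from 80% to about 70% or 60%.

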### **3.8 Target Accrual**

A total of 54 patients will be enrolled to the study. This includes 2 to 18 patients (up to 6 per dose cohort at 400, 600 and 800 mg of HCQ daily and 6 at the RP2D, but as few as 2 patients in the unlikely event that the first 2 patients experience DLT at the lowest dose of HCQ (400 mg daily) and the study is halted.) in the Phase I metastatic portion, 6 patients for neo-adjuvant Phase II Part 1 and 30 patients for the Phase II Part 2 portion (25 needed for statistical plan and 5 expected to drop out). This does not account for replaced patients (as stated in Sections 3.6 and 3.7).

## **4.0 PATIENT SELECTION**

### **4.1 Inclusion Criteria**

Patient eligibility criteria include all of the following:

1. Signed written informed consent.
2. Diagnosis of estrogen positive breast cancer, estrogen receptor-positive and HER2-negative by ASCO/CAP criteria.
3. ECOG performance status 0-1.
4. Female and age  $\geq$  18 years and postmenopausal defined by:
  - a. Age  $\geq$  55 years and 1 year or more of amenorrhea.
  - b. Age < 55 years and 1 year or more of amenorrhea with LH and/or FSH levels in the postmenopausal range.
  - c. Age < 55 with prior hysterectomy but intact ovaries with LH and/or FSH levels in the postmenopausal range
  - d. Chemotherapy or medically induced ovarian suppression with 1 year or more of amenorrhea and with LH and/or FSH levels in the postmenopausal range.
  - e. Status after bilateral oophorectomy ( $\geq$  28 days prior to first study treatment).
5. Adequate hematological, renal, hepatic function defined as follows:
  - a. ANC  $\geq$  1500 cells/ $\mu$ l.
  - b. Platelet count  $\geq$  100,000/ $\mu$ l.

- c. Serum creatinine concentration < 1.5 x ULN.
- d. Bilirubin level < 1.5 x ULN.
- e. Aspartate aminotransferase (AST) or alanine aminotransferase (ALT) <3 x ULN or alkaline phosphatase ≤ 2.5 ULN.

6. Metastatic cohorts (Phase I): Diagnosis of Stage IV estrogen positive breast cancer, estrogen receptor-positive and HER2-negative by ASCO/CAP criteria.
7. Metastatic cohorts (Phase I): Must be a candidate for treatment with CDK4/6 inhibitor and endocrine therapy with an aromatase inhibitor as standard of care.
8. Metastatic cohorts (Phase I): No prior exposure to CDK 4/6 inhibitors.
9. Neoadjuvant cohorts (Phase II): Diagnosis of Stage I-III estrogen positive breast cancer, estrogen receptor-positive and HER2-negative by ASCO/CAP criteria. If Stage I, clinical tumor size must be ≥1.5 cm.
10. Neoadjuvant cohorts (Phase II): Baseline tumor Ki67 > 5%.
11. Neoadjuvant cohorts (Phase II): Surgical candidate and appropriate for pre-operative endocrine therapy.

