## 7.0 ADVERSE EVENT MONITORING AND REPORTING

### 7.1 Definition of an Adverse Event

An adverse event is the appearance or worsening of any undesirable sign, symptom, or medical condition occurring after starting the study drug even if the event is not considered to be related to study drug. Medical conditions/diseases present before starting study drug are only considered adverse events if they worsen after starting study drug. Abnormal laboratory values or test results constitute adverse events only if they induce clinical signs or symptoms, are considered clinically significant, or require therapy.

Attribution	Grade 1	Grade 2	Grade 3	Grade 4	Grade 5
Unrelated	Phase I	Phase I	Phase I	Phase I	Phase I
			Phase II	Phase II	Phase II
				Phase III	Phase III
Unlikely	Phase I	Phase I	Phase I	Phase I	Phase I
			Phase II	Phase II	Phase II
				Phase III	Phase III
Possible	Phase I	Phase I	Phase I	Phase I	Phase I
	Phase II	Phase II	Phase II	Phase II	Phase II
		Phase III	Phase III	Phase III	Phase III
Probable	Phase I	Phase I	Phase I	Phase I	Phase I
	Phase II	Phase II	Phase II	Phase II	Phase II
		Phase III	Phase III	Phase III	Phase III
Definitive	Phase I	Phase I	Phase I	Phase I	Phase I
	Phase II	Phase II	Phase II	Phase II	Phase II
		Phase III	Phase III	Phase III	Phase III

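### Inclusion item 5e joins the AST, ALT and alkaline phosphatase limits by 'or', so read literally it can admit a patient with no cap on the transaminases

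*Combined protocol and SAP*

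**What the plan says.** Section 4.1 opens with "Patient eligibility criteria include all of the following". Item 5 then asks for adequate hematological, renal and hepatic function, defined by sub-items a to e. Two of these concern the liver:

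- Item 5d: "Bilirubin level < 1.5 x ULN".
- Item 5e: "Aspartate aminotransferase (AST) or alanine aminotransferase (ALT) <3 x ULN or alkaline phosphatase ≤ 2.5 ULN".

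None of the exclusion criteria in section 4.2 sets a transaminase limit or names liver disease.

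The DLT definition in section 3.3 includes "Any grade 3 or higher non-hematologic toxicity" and "Liver function abnormalities meeting Hy's law". It then adds: "All AEs of the specified grades should count as DLTs except those that are clearly and incontrovertibly due to disease progression or extraneous causes". It makes no provision for a patient whose liver tests were abnormal at baseline.

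Section 7.1 narrows what is an adverse event in the first place: "Medical conditions/diseases present before starting study drug are only considered adverse events if they worsen after starting study drug". For laboratory findings it says: "Abnormal laboratory values or test results constitute adverse events only if they induce clinical signs or symptoms, are considered clinically significant, or require therapy".

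**The concern.** An eligibility criterion is applied as written. As written, item 5e does not secure what item 5 says it defines, because a patient can satisfy it on alkaline phosphatase alone with AST and ALT at any level.

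The documents themselves treat the liver as a risk. Hy's law is a DLT (section 3.3), a reason for permanent discontinuation (section 6.1.4) and an SAE criterion (section 7.2). The hydroxychloroquine insert (Appendix B, general precautions) advises caution in hepatic disease. The palbociclib insert (Appendix A, Table 5) reports raised AST in 52% and raised ALT in 43% of patients on palbociclib plus letrozole, against 34% and 30% on placebo plus letrozole. Those figures are for 125 mg/day, so they may not carry over to the 75 mg used here. Section 1.3 describes Phase I as the very first exposure to the combination, and item 5 also governs the early-stage patients in Phase II.

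There is a second, narrower consequence for the Phase I endpoint. If a patient enters with raised enzymes and these worsen on treatment, the event can become a DLT, and section 3.3 gives no rule for separating the drug's contribution from the starting level.

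**Working it through.** The plan states no figure on this point, so there is none to reproduce. The check is of logic, with one conditional illustration.

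**1. What item 5e admits.** Each of the three enzymes is either within its limit or not, giving 2 × 2 × 2 = 8 combinations.

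| AST within | ALT within | Alk. phos. within | As written | (AST or ALT) and alk. phos. | All three |
|---|---|---|---|---|---|
| yes | yes | yes | eligible | eligible | eligible |
| yes | yes | no | eligible | no | no |
| yes | no | yes | eligible | eligible | no |
| yes | no | no | eligible | no | no |
| no | yes | yes | eligible | eligible | no |
| no | yes | no | eligible | no | no |
| no | no | yes | eligible | no | no |
| no | no | no | no | no | no |
| | | **Eligible** | **7 of 8** | **3 of 8** | **1 of 8** |

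These are counts of logical combinations, not patient frequencies. The second-to-last combination is the important one: both transaminases over the limit, alkaline phosphatase within it. That patient is eligible as written and ineligible under either stricter reading. The middle reading, which changes only the second 'or', still leaves one transaminase uncapped when the other is within its limit.

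**2. Whether another criterion closes the gap.** Item 5d caps bilirubin separately and is always required. No criterion in sections 4.1 or 4.2 caps AST or ALT.

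**3. Whether an abnormal baseline can become a DLT.** Taking sections 3.3 and 7.1 together:

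- Section 3.3 counts adverse events of the specified grades.
- A raised enzyme that stays where it was at entry is not an adverse event under section 7.1, and so not a DLT.
- A raised enzyme that worsens to grade 3 in the 28-day DLT window, and is symptomatic, clinically significant or treated, is an adverse event and meets the grade 3 non-hematologic rule.
- It escapes only if clearly and incontrovertibly due to progression or extraneous causes.

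**4. What one such event would do to the 3+3 rule (illustration only).** The documents give no true DLT rate, so p is an assumption. A level is not tolerated at two or more DLTs among up to six patients:

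- Without a non-drug DLT: P = P(≥2 of first 3) + P(1 of first 3) × [1 − (1 − p)³]. At p = 10%: 0.028 + 0.243 × 0.271 = 0.094.
- Given one non-drug DLT among the first three: P = 1 − (1 − p)⁵, since any DLT in the other five is enough. At p = 10%: 1 − 0.9⁵ = 0.410.

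| Assumed p | 5% | 10% | 15% | 20% | 25% |
|---|---|---|---|---|---|
| No non-drug DLT | 2.7% | 9.4% | 18.6% | 29.1% | 40.0% |
| One non-drug DLT in first three | 22.6% | 41.0% | 55.6% | 67.2% | 76.3% |

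The second row assumes that the event has already happened. It shows how sensitive a 3+3 design is to one misattributed DLT; it does not measure the effect of item 5e.

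**The case against.** The best defence is that item 5e does not stand alone. Bilirubin is capped separately. Phase I patients must be candidates for a CDK4/6 inhibitor with an aromatase inhibitor as standard of care (item 7), and acute illness is excluded (section 4.2, item 3). Liver tests are done at baseline and weekly for eight weeks in Phase I (section 5.2). The principal investigator reviews data before each escalation (section 3.2), and IND Office approval is needed to change dose level (section 8.1). Investigators may also read 5e strictly in practice. All of this narrows the safety gap. None of it puts a limit on AST or ALT, and differing strictness between investigators would make eligibility inconsistent.

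Several stronger readings are tempting and are not supported:

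- A reader might infer that one normal value admits the patient. The limits are multiples of ULN, so the passing value need only be within its limit.
- A reader might infer that liver abnormalities present at entry count as DLTs, so that two such patients could settle the RP2D. Section 7.1 rules this out for a stable abnormality. The route needs worsening, grade 3, and symptoms, clinical significance or treatment; a worsening on treatment is also not self-evidently unrelated to the drug.
- A reader might infer that the opening line of section 4.1 already requires every enzyme limit. It joins the numbered items, but the sub-items of item 4 under the same line are plainly alternatives, so it does not settle the logic inside 5e.

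**Conclusion.** The wording fault is real and nothing elsewhere in the protocol corrects it. Followed literally, item 5e leaves AST and ALT uncapped whenever alkaline phosphatase is within its limit, contrary to the purpose stated at the head of item 5. It should be corrected, but it does not invalidate the design.

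The safety gap is bounded by the separate bilirubin limit. The effect on Phase I is conditional on a raised baseline that worsens as described. Its frequency cannot be estimated, because the documents give no distribution of baseline liver tests and no expected DLT rate. The Phase II Simon design, its alpha and its power do not depend on this point.

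**What to change.** Reword item 5e so that it no longer leaves the transaminases uncapped. Either replace both uses of 'or' so that each listed limit must be met, or, if the sponsor intends an alternative combination (for example for alkaline phosphatase in patients with bone disease, whom section 5.2.8 allows in Phase I), write that combination out in full. Changing only the second 'or' is not enough, as the table shows. The thresholds and the combination are the sponsor's decision.

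If the chosen wording still allows raised baselines, section 3.3 should say how a liver DLT is judged in such a patient; the content of that rule is also for the sponsor.

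The cost is a one-line amendment using tests already scheduled at baseline. Some patients may be screened out; the documents do not allow the number to be estimated.
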